3.1.2. Part B: Expansion

Part B is designed to further evaluate the safety and antitumor activity of the combination of LV and pembrolizumab and to maximize the benefit-risk profile. This part of the study will be conducted in 2 cohorts. Patients will enroll sequentially into Cohort 1 followed by Cohort 2. Part B Cohort 1 will receive the MAD of LV 2.5 mg/kg, (capped at 100 kg) in combination with pembrolizumab. Part B Cohort 2 will receive a dose of LV 2.0 mg/kg (capped at 100 kg), in combination with pembrolizumab (see Section 3.2.3.1 for rationale of Part B Cohort 2). Patients receiving >200 mg LV per infusion are required to be administered prophylactic granulocyte-colony stimulating factor (G-CSF).

Patients will receive LV and pembrolizumab q3wk. Pembrolizumab, 200 mg IV will be given per the US prescribing information on the same day as LV, approximately 60-90 minutes following LV infusion.

Approximately 73 patients will be enrolled in Part B of the study (approximately 48 in Cohort 1 and approximately 25 in Cohort 2).

The SMC and ISMC will continue to monitor the safety of LV and pembrolizumab. The SMC will meet regularly during Part A but convene as needed in Part B. The ISMC will meet periodically.

3.1.3. Part C: Weekly LV dosing

Part C will test weekly (q1wk) dosing of LV administered on Day 1, Day 8, and Day 15 of every 21-day cycle not to exceed 200 mg per infusion in combination with pembrolizumab administered on Day 1 of every cycle.

Part C will consist of

- Dose escalation cohorts
- Expansion cohorts

Up to approximately 64 patients may be enrolled in Part C. The totality of data from all patients in dose escalation and expansion cohorts will be used to determine the recommended q1wk LV dose in combination with pembrolizumab.

Dose escalation will begin at dose level 0. The first 2 patients enrolled at each dose level will be evaluated for DLTs. If LV dose level 0 clears DLT evaluation, subsequent patients may be enrolled at dose level 1 or in the dose level 0 expansion cohorts. See Table 2 for dose levels and Section 3.2.1 for details on assigning patients to treatment groups.

3.1.3.1. Part C: Dose Escalation Cohort

The starting dose of LV will be dose level 0 at 1.0 mg/kg on Day 1, Day 8, and Day 15. Planned dose levels are shown in Table 1. Pembrolizumab will be administered on Day 1 approximately 60 to 90 minutes after infusion of LV is complete.

Only 1 dose escalation cohort will be open at a time. DLT evaluation will only include data from dose-escalation cohorts and will be assessed according to the DLT criteria in Section 3.1.5. Other dose levels may be evaluated based on the totality of the safety data and/or recommendations from the SMC.

The SMC will monitor safety during dose escalation in Part C and may recommend expansion of any cohort to further evaluate the safety at a given dose or enrollment of additional cohorts to investigate intermediate or additional dose levels of LV. The SMC will continue to review cumulative safety data in order to identify safety concerns that may emerge due to cumulative exposure, after the DLT window, or at a low frequency. In addition, the SMC will assess AE data from patients in dose-expansion cohorts to identify safety signals. For more details, see Section 7.5.1.

Dose escalation will be guided by the modified toxicity probability interval (mTPI) method (Ji 2010). The mTPI method is a model-based dose-escalation design that uses a Bayesian statistical framework and a beta-binomial hierarchic model (see Appendix M for more details and scenarios). Using a target DLT rate of 25% with a 5% margin, the dosing-decision rules are:

- Escalate if current DLT rate is most likely <20%
- Continue if current DLT rate is most likely between 20% and 30%
- De-escalate if current DLT rate is most likely >30%

Each dose cohort will start with 2 patients. The SMC will evaluate the safety of each dose-level cohort and make dose escalation/de-escalation recommendations using the decision matrix in Table 2. Escalation to the next dose level will occur if 0 of 2 evaluable patients encounter a DLT. If 1 of 2 evaluable patients encounter a DLT, an additional 4 patients will be accrued (total of 6 DLT-evaluable patients). If 2 of 2 evaluable patients at a dose level encounter a DLT, further evaluation of that dose level may be allowed if recommended by the SMC. Escalation to the next dose level will occur if ≤1 of 6 evaluable patients encounter a DLT (see Table 2, column 5). The

MTD will be estimated based on data from all patients across all evaluated dose levels (Appendix M). If no doses are safe, dose escalation will stop, and no MTD will be declared.

The sponsor (in consultation with the SMC) may, for safety reasons, override the model's allocation of a patient to a particular dose level.

Table 1: Planned dose levels for Part C (q1wk LV dosing)

Dose Level	Weekly LV Dose (mg/kg/wk)	Maximum LV dose in a 3-week cycle (mg/kg/cycle)
0	1.00	3.00
1	1.25	3.75

The maximum dose will be 200 mg per infusion at all dose levels.

Table 2: mTPI decision matrix

Number of DLT-Evaluable Patients Treated at Current Dose									
		2	3	4	5	6	7	8	9
Ts	0	E	E	E	E	E	E	E	E
with DLTs	1	S	S	S	S	E	E	E	E
vith	2	Da	D	D	S	S	S	S	S
-	3		DU	DU	DU	D	S	S	S
tien	4			DU	DU	DU	DU	DU	D
of Patients	5				DU	DU	DU	DU	DU
	6					DU	DU	DU	DU
Number	7						DU	DU	DU
N	8						·	DU	DU
	9								DU

E=Escalate to the next higher dose, S=Stay at the current dose, D=De-escalate to the next lower dose, DU=Current dose is unacceptably toxic.

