APPENDIX M: MODIFIED TOXICITY PROBABILITY INTERVAL DESIGN SIMULATION REPORT

Introduction

Part C of this study evaluates weekly (q1wk) LV dosing (Day 1, Day 8, and Day 15 of every 3-week cycle). The primary objective of Part C is to evaluate the safety, tolerability, and identify the recommended dose of LV. Toxicity is measured by dose-limiting toxicities (DLTs) observed within the first cycle. Dose escalation in Part C will be conducted according to a modified toxicity probability interval method (mTPI).

DOSE ESCALATION

Overview

There will be 2 selected dose levels for LV in Part C. Intermediate doses of LV may also be evaluated during the execution phase at the discretion of the sponsor upon recommendation by the Safety Monitoring Committee (SMC).

The starting dose level of LV is 1.0 mg/kg. Dose escalation is conducted according to an mTPI method and according to a set of rules governing entry into the study and assignment of dose level. Decisions are described in Section 3.1.3 of the study protocol and detailed in this appendix. They are based on the posterior distribution of the DLT rate and derived independently for each dose level. The trial is closely monitored for safety and for identification of the MTD. If the SMC recommends exploration of an intermediate dose level, an additional dose level may be added.

Modified Toxicity Probability Interval Method

Dose escalation is conducted using the modified toxicity probability interval method. The implementation programs are available at: https://udesign.laiyaconsulting.com/.

For each dose level, i, the probability of a DLT on dose i is denoted by pi. The target toxicity probability in this study is defined as 25%, with a 5% margin. The equivalence interval is [20%, 30%], which contains the doses close to the true target DLT rate that physicians would deem acceptable for treating future patients. The equivalence interval partitions the unit interval (0, 1) into 3 subintervals: (0, 20%), [20%, 30%], and (30%, 1). Doses in these 3 intervals correspond to:

- Under dosing: pi <20%
- Proper dosing: 20% ≤ pi ≤30%
- Over dosing: pi >30%

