In each dose level, the prior distribution of DLT probability, pi, is assumed to be non-informative Beta(1, 1). After each patient is treated and assessed for DLT, the posterior distribution of pi is updated to Beta(1 + xi, 1 + ni - xi), where xi and ni denote the number of DLTs and the number of DLT-evaluable patients at dose level i, respectively. The dose-escalation decision is based on the unit probability mass (UPM) on the posterior distribution of pi. For a given interval [a, b], the

UPM is defined as the ratio of the probability of the interval to the length of the interval, where for any DLT probability pi and

$$0 \le a < b \le 1$$

$$UPM(a, b) = Pr(a < pi < b) / (b - a)$$

After the toxicity outcomes are observed, the UPM on (0, 20%), [20%, 30%], and (30%, 1) at the current dose is calculated, and the dosing decision rules are:

- Escalate (E), if (0, 20%) has the largest UPM
- Stay at the current dose (S), if [20%, 30%] has the largest UPM
- De-escalate (D), if (30%, 1) has the largest UPM

In addition, the toxicity of a dose is defined as being unacceptable if there is more than a 95% probability that the DLT rate is higher than 25%,

Toxicity at dose i is unacceptable: Pr(pi >25%) >95%

If dose level i is determined to be unacceptable, the next patients are treated at dose level i-1 and doses i and higher are excluded from the trial. If i=1, the trial is terminated, and it is concluded that no dose level is safe, if there are no lower dose levels of interest to explore. The decision rules for each dose level are provided in Table 13.

Table 13: Decision rules for SGNLVA-002 – Part C, by mTPI for each dose level with target MTD = 25%

	Number of DLT-Evaluable Patients Treated at Current Dose									
		2	3	4	5	6	7	8	9	
	0	E	E	E	E	E	E	E	E	
8	1	S	S	S	S	E	E	E	E	
citi	2	Da	D	D	S	S	S	S	S	
Number of Toxicities	3		DU	DU	DU	D	S	S	S	
ofT	4			DU	DU	DU	DU	DU	D	
oer o	5				DU	DU	DU	DU	DU	
T T	6					DU	DU	DU	DU	
Z	7						DU	DU	DU	
	8							DU	DU	
	9								DU	

E=Escalate to the next higher dose, S=Stay at the current dose, D=De-escalate to the next lower dose, DU=Current dose is unacceptably toxic

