At the end of the trial when the toxicity outcomes of all the enrolled DLT-evaluable patients are observed, a dose will be selected as the estimated MTD. The estimation is separated from the design for dose finding. The MTD is selected by performing an isotonic regression that borrows strength across doses. Let $\hat{p}i$ be the posterior mean of DLT rate. The pooled adjacent violators algorithm (PAVA) is applied on $\hat{p}i$ so that the resulting transformed values $\hat{p}i^*$ increase with the

a Dose will be de-escalated if the first 2 DLT-evaluable patients in a dose level experience DLT. Further evaluation of that dose level may be allowed if recommended by the SMC.

dose levels. That is, $\hat{p}i^* \le \hat{p}i+1^*$ for all i. The recommended MTD is the highest dose with a toxicity probability $\hat{p}i^*$ less than or equal to the target DLT rate 25%, i.e.,

Estimated MTD = max $\{i: \hat{p}i \le 25\%\}$

Dose-Escalation Rules

- 1. Dose escalation begins with patient enrollment to dose level of 1.0 mg/kg. At least 2 DLT-evaluable patients per dose level are required to escalate at any dose level. Once all patients in the previous cohort have completed DLT evaluation, patients can be enrolled to the next dose-level cohort. Subsequent enrollment and dose selection occurs via the following rules:
- If a dose level i is unacceptable, de-escalate to the lower dose level and never treat future
 patients at level i. If i = 1, stop the trial and conclude no dose is safe.

Interim Monitoring

The dose escalation will be closely monitored for safety and for identification of the MTD. If no doses are safe, dose escalation for that population will stop, and no MTD will be declared.

Safety Monitoring

If no doses are safe, dose escalation will stop, and no MTD will be declared. Formally, if

[figure not shown]
Pr(pi >25%) >95% for all i

Identification of the MTD

After each dose-level cohort, the estimation of MTD will be performed. If the model's next recommended dose is the same or below the MTD, the dose escalation may be stopped and MTD can be declared. Alternatively, if the model's next recommended dose is above the estimated MTD level, and patients have already been treated at the higher dose level, and the observed DLT rate at the recommended higher dose level exceeds the target DLT rate of 25%, the dose escalation may also be stopped and MTD can be declared.

Simulation Studies

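### At 2 DLTs in 2 patients, Appendix M's exclusion rule and the Part C decision tables disagree, and the block of 4 after 1 in 2 is not tied to the n=3 to 5 table columns

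*Protocol*

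**What the plan says.** Protocol Section 3.1.3.1 starts each Part C dose level with 2 evaluable patients and has the SMC decide from Table 2.

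- **After 1 DLT in 2:** "an additional 4 patients will be accrued (total of 6 DLT-evaluable patients"). No look inside the block is mentioned.
- **After 2 DLTs in 2:** "If 2 of 2 evaluable patients at a dose level encounter a DLT, further evaluation of that dose level may be allowed", subject to an SMC recommendation. Tables 2 and 13 mark this cell Da. Footnote a, the same in substance under both tables, makes de-escalation the default and repeats the SMC exception.

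Appendix M gives the model behind the tables. "The target toxicity probability in this study is defined as 25%, with a 5% margin". The prior at each level is Beta(1,1). "After each patient is treated and assessed for DLT, the posterior distribution of pi is updated". The exclusion rule reads "Toxicity at dose i is unacceptable: Pr(pi >25%) >95" per cent. When it is met, "the next patients are treated at dose level i-1 and doses i and higher are excluded from the trial". The list headed Dose-Escalation Rules adds the instruction to "de-escalate to the lower dose level and never treat future" patients at that level.

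Appendix M gives two versions for the lowest level. The method subsection ends the trial only if no lower level is of interest. The Dose-Escalation Rules stop it without that condition.

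**The concern.** A stated safety threshold should give one answer for one set of data. Two DLTs in two patients is the strongest toxicity signal a starting cohort can produce. At that point the rule text closes the dose, while the tables and Section 3.1.3.1 leave a route to further dosing there. A committee member working from the rule text and one working from the tables could reach different decisions about the next patient.

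The block of 4 raises a related question. Tables 2 and 13 have columns for 3, 4 and 5 patients, and some of their cells call for de-escalation or exclusion. A commitment to reach 6 patients, with no stated look, leaves open whether those cells bind while the block is filling. Both points also bear on which rule the Appendix M operating characteristics describe.

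**Working it through.** **Inputs.** From Appendix M: Beta(1,1) prior, posterior Beta(1+x, 1+n−x) for x DLTs in n patients, intervals below 20%, 20–30% and above 30%, and exclusion (DU) if Pr(p>25%) > 95%. From Section 3.1.3.1: starting cohort of 2, block of 4 after 1/2. True DLT rates used: 25% (the target) and 40% (a value simulated for 1.25 mg/kg in Appendix M).

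**Step 1: reproduce the plan's table.** For each of the 52 cells (n = 2 to 9), take the interval with the largest unit probability mass (UPM), then apply the 95% rule. Fifty cells reproduce. This counts 1/2 as S, since stay and de-escalate tie exactly there (UPM 1.12 each). The two that differ are 2/2 and 1/6. At 1/6 the table says E, but UPM favours S (2.473 against 2.116); that is a separate matter.

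**Step 2: posterior probability at the cells that matter.**

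| DLTs/n | Posterior | Pr(p>25%) | Above 95%? | Tables 2 and 13 |
|---|---|---|---|---|
| 1/2 | Beta(2,2) | 0.8438 | no | S |
| 2/2 | Beta(3,1) | 0.9844 | **yes** | **Da** |
| 2/3 | Beta(3,2) | 0.9492 | no | D |
| 2/4 | Beta(3,3) | 0.8965 | no | D |
| 2/5 | Beta(3,4) | 0.8306 | no | S |
| 3/4 | Beta(4,2) | 0.9844 | yes | DU |
| 3/5 | Beta(4,3) | 0.9624 | yes | DU |
| 4/5 | Beta(5,2) | 0.9954 | yes | DU |

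For 2/2 the value is 1 − 0.25³ = 0.9844. It equals the value at 3/4 and exceeds that at 3/5, yet only 2/2 escapes DU.

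**Step 3: how often 2/2 arises.** The probability is p²: 0.25² = 6.3% and 0.40² = 16.0%.

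**Step 4: the block of 4, given 1/2.** Assume each result is known before the next patient is dosed and the block continues to 6.

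- DU at n=4 (3/4) needs DLTs in both of the next two patients: p².
- DU first at n=5 (3/5) needs one DLT in the next two, then another: 2p²(1−p). The 4/5 cell is reached only through 3/4.
- Probability of DU before the sixth patient: p² + 2p²(1−p). At 40%: 0.160 + 0.192 = 0.352. At 25%: 0.0625 + 0.0938 = 0.156.
- Patients dosed after DU, averaged over all 1/2 cohorts (two remain after n=4, one after n=5): 2p² + 2p²(1−p). At 40%: 0.320 + 0.192 = 0.51. At 25%: 0.125 + 0.094 = 0.22.
- The same, given that DU occurs: 0.512/0.352 = 1.45 at 40%, and 0.219/0.156 = 1.40 at 25%.

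**The case against.** The strongest defence is that 2/2 is a deliberate, labelled special case. Section 3.1.3.1, both tables and both footnotes agree on it. De-escalation is the default, and further evaluation needs an SMC recommendation. This stands in part. It rules out a reading in which Section 3.1.3.1 alone departs from Appendix M, or in which continued dosing is openly permitted. It does not remove the conflict, because Appendix M's threshold and never-treat instruction carry no exemption for 2/2.

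A reader might also infer that the exception breaches the clause letting the sponsor, "for safety reasons, override the model's allocation of a patient to a particular dose level". The documents do not support that. The clause governs the sponsor's override of the model's allocation; the 2/2 exception is a separate SMC provision.

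On the block, the defence is that the text is silent and does not forbid looks. The same paragraph has the SMC use Table 2, the posterior is updated patient by patient, and safety is closely monitored. This stands to the extent that one cannot say the n=3 to 5 cells are never applied. What remains is that nothing says they must be.

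A larger size is tempting if D calls are counted. At 40%, a D call occurs by n=4 in 0.40 + 0.60×0.40 = 64% of 1/2 cohorts, with 3p + 2p(1−p) = 1.68 patients per 1/2 cohort dosed after it. But D at 2/3 or 2/4 is not exclusion. Of those cohorts, 2p(1−p)²/0.64 = 0.288/0.64 = 45% would reach 2/5, which Table 2 calls S. These figures do not measure dosing at an excluded level.

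Finally, the practical effect may be spent. Section 9.1.3 treats 1.25 mg/kg as the selected level, and Section 3.2.3.2 reports 17 patients on weekly LV with pembrolizumab by December 2020. This lowers the severity. The rule is still live on paper, because Section 3.1.3.1 lets other levels be evaluated.

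**Conclusion.** The point holds in limited form. At 2/2 the Appendix M rule text excludes the dose (98.4% against a 95% limit), while Tables 2 and 13, footnote a and Section 3.1.3.1 do not. The contradiction lies inside Appendix M as well as between it and the body text. The two Appendix M statements on stopping at the lowest level also differ. It would go too far to say flatly that the plan ends the trial at 2/2 on the lowest dose, since one of those statements is conditional.

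The block of 4 is a gap in specification. It matters in 35% of 1/2 cohorts at a true rate of 40%, and 16% at 25%. On average 0.5 and 0.2 patients per 1/2 cohort are dosed after exclusion is reached. These figures rest on results arriving one patient at a time, which no passage states. If the four are dosed concurrently within the 21-day DLT window, the excess tends to zero.

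The point is worth correcting because it concerns a stated safety threshold. Severity is low if Part C escalation is complete, which the documents suggest but do not state.

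**What to change.** 1. Reconcile Section 3.1.3.1, Tables 2 and 13 with footnote a, and the Appendix M exclusion text into one rule for 2/2. Cover the lowest dose, where the two Appendix M statements also need to agree. Which rule is right is for the sponsor and the SMC.
2. Reconcile the block of 4 with the n=3, 4 and 5 columns by stating whether those cells bind as DLT results arrive.
3. State that the Appendix M operating characteristics were produced under the reconciled rule, or rerun them. The readable text of Appendix M gives neither the cohort size nor the maximum sample size simulated, so this could not be checked here.

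The cost is wording in one section, two footnotes and Appendix M, and at most a rerun of an existing simulation. If Part C escalation is complete, a clarifying note recording which rule was applied would serve most of the purpose.

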3.1.4. Part D: Day 1 and Day 8 every 21-days LV dosing

Part D will assess LV 1.5 mg/kg administered on Day 1 and Day 8 (off Day 15) of every 21-day cycle, not to exceed 200 mg per infusion, in combination with pembrolizumab administered on Day 1 of every cycle. Approximately 40 patients with PD-L1 CPS<10 will be enrolled in Part D. Ongoing, real-time, continuous review of patient safety and SAEs will be conducted by the sponsor's Drug Safety Department. Additionally, the ISMC will ensure periodic safety data review throughout the study.

a Dose will be de-escalated if the first 2 DLT-evaluable patients in a dose level experience a DLT. Further evaluation of that dose level may be allowed if recommended by the SMC.

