9.1.3. Part C

In Part C, it is estimated that approximately 4 to 12 patients (assuming evaluation of 2 dose levels) will be treated in dose escalation. Operating characteristics of the dose escalation design, including the average number of patients allocated to each dose across a variety of toxicity scenarios, are presented in the simulation report (Appendix M).

Up to approximately 64 patients may be enrolled across the dose escalation and expansion cohorts in Part C (assuming 2 patients in each of the dose escalation cohort of 1.0 and 1.25 mg/kg, and 60 patients in the expansion cohort at the selected dose level of 1.25 mg/kg).

Table 9 summarizes the 2-sided 95% exact CIs among 62 patients at 1.25 mg/kg (2 in dose escalation and 60 in dose expansion cohort) assuming the observed ORR is between 50% and 70%.

Table 9: 2-sided 95% exact confidence intervals for Part C

Number of confirmed Objective Responses	Confirmed ORR(%)	95% exact CI (N=62)
31	50%	37%, 63%
37	60%	46%, 72%
43	69%	56%, 80%

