To evaluate the operating characteristics of the dose-escalation design, simulation studies were performed for the following scenarios.

[figure not shown]

The plots illustrate the true DLT rate at each dose level. For Part C simulation, dose level 1 is 1.0 mg/kg and dose level 2 is 1.25 mg/kg. For example, Scenario 1 assume that MTD is 1.25 mg/kg, Scenario 2 assume that MTD is 1.0 mg/kg, and Scenario 3 assume that no selected dose is safe.

In each scenario, the dose-escalation and MTD-estimation process is replaced with 1000 replications. The probability of selecting an MTD, average number of DLT and the average number of patients treated, at each dose level is provided.

[figure not shown]
Amendment 11: 19-Oct-2023

Page 124 of 152

[figure not shown]
	Possible MTD Dose	Possible MTD Dose Level						
Scenario 1: MTD is 1.25 mg/kg	No dose is safe	1.0 mg/kg	1.25 mg/kg					
True DLT rate		0.12	0.22					
Mean number of patients at dose level		4.20	5.27					
				P (Select the True MTD) = 0.53				
Mean number of DLTs		0.52	1.19	Average DLT rate = 0.19				
at dose level				Average number of patients				
Pr (Chosen MTD)	0.10	0.37	0.53	above MTD = NA				

Pr=probability

Study SGNLVA-002 Clinical Protocol Ladiratuzumab Vedotin (LV; SGN-LIV1A) Seagen Inc. - Confidential

	Possible MTD Dose	Possible MTD Dose Level						
Scenario 1: MTD is 1.0 mg/kg	No dose is safe	1.0 mg/kg	1.25 mg/kg					
True DLT rate		0.22	0.40					
Mean number of patients at dose level		5.50	3.89					
Mean number of DLTs		1.23	1.57	P (Select the True MTD) = 0.49				
at dose level		1.23	1.57	Average DLT rate = 0.34 Average number of patients				
Pr (Chosen MTD)	0.35	0.49	0.16	above MTD = 3.9				

	Possible MTD Dose	Possible MTD Dose Level						
Scenario 1: MTD is 1.0 mg/kg	No dose is safe	1.0 mg/kg	1.25 mg/kg					
True DLT rate		0.35	0.4					
Mean number of patients at dose level		4.87	2.48	D.C. 1. 41 T. 3. 5770 314				
Mean number of DLTs at dose level		1.75	0.96	P (Select the True MTD) = NA Average DLT rate = 0.47 Average number of patients				
Pr (Chosen MTD)	0.62	0.25	0.13	above MTD = NA				

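### Part C prints Escalate at 1 DLT in 6, but Appendix M's stated mTPI rule gives Stay there, and no footnote marks the departure

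*Protocol*

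**What the plan says.** Section 3.1.3.1 starts each Part C escalation cohort with 2 patients and tells the safety monitoring committee (SMC) to use Table 2. If 1 of the first 2 has a DLT, 4 more are enrolled. Then: "Escalation to the next dose level will occur if ≤1 of 6 evaluable patients encounter a DLT (see Table 2, column 5". The fifth column of Table 2 is n=6. Its entry for 1 DLT is E, and Table 13 in Appendix M prints the same. Table 13 is titled as the mTPI decision rules for a 25% target.

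Appendix M gives the rule. "The target toxicity probability in this study is defined as 25%, with a 5% margin", so the cut points are 20% and 30%. The prior is Beta(1,1), and UPM is an interval's posterior probability divided by its length. The interval with the largest UPM decides, for example: "Stay at the current dose (S), if [20%, 30%] has the largest UPM". A dose is unacceptable (DU) if Pr(p>25%) exceeds 95%.

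The only footnote to either matrix is footnote a, on the 2-of-2 cell: "Dose will be de-escalated if the first 2 DLT-evaluable patients in a dose level experience a DLT". The 1-of-6 cell has no note.

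**The concern.** A matrix presented as the output of a stated rule should follow from that rule, or say where it does not. Here one cell does not follow, and it errs towards a higher dose. It is also a planned decision point: on the branch that starts with 1 of 2, a DLT has already occurred, so 1 of 6 is the best result possible and the only one that escalates at n=6.

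Two things are at stake. One is whether a patient group at 1.0 mg/kg moves to 1.25 mg/kg or stays. The other is whether the operating characteristics in Appendix M describe the design as printed, because the appendix does not say whether the simulations used the UPM rule or the printed matrix.

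**Working it through.** **Inputs (Appendix M).** Posterior Beta(1+x, 1+n−x) for x DLTs in n patients; intervals (0, 0.20), [0.20, 0.30], (0.30, 1), with lengths 0.20, 0.10 and 0.70.

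**The cell 1 of 6.** The posterior is Beta(2,6), with F(t) = 1 − (1−t)^7 − 7t(1−t)^6.

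- F(0.20) = 1 − 0.2097 − 0.3670 = 0.4233; UPM = 0.4233/0.20 = 2.116
- F(0.30) = 1 − 0.0824 − 0.2471 = 0.6706; UPM = (0.6706 − 0.4233)/0.10 = 2.473
- Remainder 0.3294; UPM = 0.3294/0.70 = 0.471

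The middle interval is largest, so the rule gives Stay. Pr(p>25%) = 0.445, so DU does not apply.

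**Other cells.** The matrix has 3+4+5+6+7+8+9+10 = 52 cells. Recomputing all of them reproduces 50.

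| DLTs/n | UPM below 20% | UPM 20–30% | UPM above 30% | Rule | Printed |
|---|---|---|---|---|---|
| 1/2 | 0.52 | 1.12 | 1.12 | S/D tie | S |
| 1/5 | 1.723 | 2.352 | 0.600 | S | S |
| 1/6 | 2.116 | 2.473 | 0.471 | S | **E** |
| 1/7 | 2.483 | 2.480 | 0.365 | E | E |
| 1/8 | 2.819 | 2.402 | 0.280 | E | E |

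The tie at 1/2 counts as agreement. The other mismatch is 2/2: the rule gives DU (Pr(p>25%) = 0.984), the table prints D, and footnote a covers it.

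**Could another rule explain the table?**

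- Margin: with target 25%, every whole-point symmetric margin from 1 to 10 gives Stay at 1/6 (2.208/2.491/0.568 at 1 point; 1.889/2.414/0.360 at 10).
- Prior, target or method: Beta(0.5,0.5), a 30% target and equal-width intervals each give E at 1/6, but leave 4, 7 and 8 mismatches (counting 2/2).
- Raw posterior probability, one reading of the bullets in Section 3.1.3.1: 42.3%/24.7%/32.9% gives E at 1/6. But 1/5 becomes 34.5%/23.5%/42.0%, which is De-escalate where S is printed; in all, 13 cells fail.

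**Size at 1.0 mg/kg.** Appendix M's three scenarios set the true DLT rate p at 12%, 22% and 35%.

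- Reaching 1/6 via 1/2: 2p(1−p) × (1−p)^4 = 2p(1−p)^5
- Escalating as printed: (1−p)^2 + 2p(1−p)^5
- Escalating under Stay, with k further patients: (1−p)^2 + 2p(1−p)^5 × (1−p)^k, since rule and table both escalate at 1/7 and 1/8, and both stay with 2 DLTs at n=6 to 9

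| | p=12% | p=22% | p=35% |
|---|---|---|---|
| Reach 1/6 | 12.7% | 12.7% | 8.1% |
| Escalate, as printed | 90.1% | 73.5% | 50.4% |
| Escalate, Stay with k=1 | 88.6% | 70.7% | 47.5% |
| Escalate, Stay with k=2 | 87.2% | 68.6% | 45.7% |
| Reduction, k=1 / k=2 (points) | 1.5 / 2.9 | 2.8 / 5.0 | 2.8 / 4.7 |

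The value of k is an assumption; the documents give no number after a Stay at n=6. Further evaluation that the SMC may allow after 2/2 is not modelled.

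**The case against.** The strongest reply is that Escalate at 1 of 6 is a deliberate rule. The sentence and both tables agree, and the 4-patient add-on can lead to escalation at n=6 only if 1 of 6 escalates. Part A also treats fewer than 2 DLTs in 6 as acceptable. If the bullet in Section 3.1.3.1 is read as the posterior mode, which is x/n under Beta(1,1), then 1/6 (16.7%) escalates and 1/5 (20%) does not, and every escalate/not-escalate cell fits. Intent is therefore plausible. But no document states it, and the mode reading fails on stay/de-escalate cells such as 1/3 and 2/6, so it does not replace Appendix M's rule.

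A reader might infer that the SMC faced two conflicting instructions. It did not: it is sent to Table 2, and the text matches. A reader might also infer that patients were escalated unsafely. The documents do not report the DLT path. Section 9.1.3 assumes 2 patients per escalation cohort, which leaves no n=6 branch, and plans for "60 patients in the expansion cohort at the selected dose level of 1.25 mg/kg".

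Safeguards exist as well. The SMC "may recommend expansion of any cohort to further evaluate the safety at a given dose", and "The sponsor (in consultation with the SMC) may, for safety reasons, override the model's allocation of a patient to a particular dose level". Either could hold the dose at 1 of 6. Neither explains a preset cell that is less cautious than the rule.

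The size is modest and does not all point one way. Appendix M says: "For example, Scenario 1 assume that MTD is 1.25 mg/kg, Scenario 2 assume that MTD is 1.0 mg/kg". In the first scenario the printed cell does slightly better, because escalation is correct there.

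**Conclusion.** The mismatch is real, confined to one cell, and minor. Under the rule as Appendix M states it, 1 DLT in 6 gives Stay (2.473 against 2.116), and the printed Escalate is the only unexplained departure in 52 cells. The cell is close to the boundary: at 1/7 the rule escalates by 2.483 to 2.480.

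It matters mainly at 1.0 mg/kg, because 1.25 mg/kg is the top planned level unless the SMC adds another. With 1 or 2 patients added after Stay, escalation falls by 1.5 to 2.9 points when the true rate is 12%, a small loss of correct escalation. At 22% and 35% it falls by 2.8 to 5.0 points, and there the dose avoided has a true DLT rate of 40%.

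That range is not an upper bound. At 1/6 the posterior mean is 2/8 = 25%, so 1.0 mg/kg on its own data meets the MTD criterion, and Appendix M would allow escalation to stop there after a Stay. The reduction would then be the whole branch: 12.7, 12.7 and 8.1 points.

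No SAP efficacy analysis is affected. Whether the simulations used the rule or the matrix cannot be checked, because Appendix M gives neither cohort size nor maximum sample size.

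**What to change.** Choose one of two; the choice belongs to the sponsor and SMC.

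- (a) Footnote 1/6 in Tables 2 and 13 as a deliberate departure from the UPM rule. Cost: one footnote, used twice.
- (b) Change 1/6 to S in both tables and replace the sentence in Section 3.1.3.1 with: if 1 of 6 has a DLT, stay and enrol further patients (state the number), then apply Table 2 at n=7 to 9. Cost: one cell in two tables, one sentence, and a decision on the number added. Making 0 of 6 the escalation threshold would not work here, since that result cannot follow 1 of 2.

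In either case, state which matrix the Appendix M simulations used, and re-run them only if it differs from the final one.

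If Part C escalation is complete, changing the cell would be retrospective. A statement in the clinical study report of which rule was applied, and whether 1 of 6 occurred, is then enough.
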